8.8 Immunogenicity

The percentage of subjects positive for each type of antibody will be summarized for each visit. Denominator for the calculation is the number of subjects in the AT population. Subjects who were tested as positive will be counted as positive for all subsequent visits. All immunogenicity data will also presented in a comprehensive data listing.

Additionally, the number and percentages of subjects who are positive at any point in time and becomes negative later will be calculated. Subjects who resolve positivity with or without medication will be presented also in a separate data listing.

Data regarding blood sample collections for antibody titers, and antibody levels for any positive tests, will be listed but not summarized.

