7 STUDY DESIGN

7.1 Overview of Study Design

Protocol CLI-06814AA1-01 is designed as a single-arm, open-label, multicenter registry study in patients with ADA-SCID requiring Revcovi as ERT. The eligible study population includes adult subjects who are currently receiving chronic ERT with Adagen, infants diagnosed via newborn screening and definitive testing for ADA deficiency, patients preparing for HSCT or HSC-GT, and patients who decline, are ineligible or do not respond to HSCT or HSC-GT.

Subjects for whom written informed consent/assent is obtained will be assigned a number and undergo enrollment procedures. The date of ICF signature is the date of enrollment into the registry. Subjects should have initial, trough erythrocyte dAXP levels and plasma ADA activity measurements collected prior to start of Revcovi as part of standard of care. Additionally, at enrollment, physical examination, vital signs, and laboratory values for total lymphocytes and subset analysis, as well as quantitative immunoglobulins, should be collected. Subjects who started treatment with Revcovi before enrollment into the CLI-06814AA1-01 study, should have data collected retrospectively in accordance with the Suggested Schedule of Assessments (Appendix 1 and Appendix 2) and in conformity to local standard of care practice.

Subjects should receive weekly IM dose(s) of Revcovi and will be followed throughout a period of at least 24-months according to the Suggested Schedule of Assessments (Appendix 1 and Appendix 2). Trough dAXP and ADA activity should be monitored throughout this treatment period, and AEs, immunogenicity, laboratory assessments, physical examination, and vital signs will also be assessed.

All Phase III STP-2279-002 participants are permitted to enroll into the CLI-06814AA1-01 registry at the time they discontinue from the Phase III STP-2279-002 study. Their first post-baseline visit in the CLI-06814AA1-01 registry will be Treatment Month 6. See the Suggested Schedule of Assessments (Appendix 1).

Enrolled subjects will be followed until the last enrolled patient has reached a minimum of 24 months of Revcovi treatment or until undergoing HSCT or HSC-GT, whichever occurs first. Subjects undergoing HSCT or HSC-GT will be followed one month after the last Revcovi dose and again at six months to assess AEs and survival.

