10.5.4 Immunogenicity

Immunogenicity should be assessed in accordance with the Revcovi PI. If testing is necessary, venous blood samples for determination of anti-Revcovi binding and neutralizing antibodies, and anti-PEG antibodies will be collected in 2-mL ethylenediaminetetraacetic acid (EDTA) tubes.

Once treatment with Revcovi has been initiated, a target trough plasma ADA activity level should be at least 30 mmol/hr/L. A decrease of ADA activity below this level suggests inadequate weight-based dosing, administration noncompliance or a development of antibodies (anti-drug, anti-PEG, and neutralizing antibodies). Antibody development to Revcovi should be suspected if a persistent fall in pre-injection levels of trough plasma ADA activity to below 15 mmol/hr/L occurs, and testing for antibodies to Revcovi should be performed.

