11.1 Enrollment

Subjects who fulfill all of the inclusion criteria and none of the exclusion criteria may be enrolled into the study. The date of ICF signature is the date of enrollment into the registry.

The following evaluations should be performed or collected retrospectively (if available) before starting Revcovi unless otherwise indicated.

- Informed assent/consent
- Demographics
- Medical history and baseline characteristics (including ADA-mutation results, if available)

- Assessment of infectious complications and hospitalizations within the past 12 months
- Concomitant medications/procedures
- Physical examination (including height and weight) from 1 year prior to start of Revcovi treatment
- Vital signs
- Safety laboratory assessments: hematology, serum chemistry, urinalysis (if available)
- Immune Function (if available)
- B-/T-/NK-lymphocyte subset
- Trough plasma ADA activity and erythrocyte dAXP
- Quantitative immunoglobulins
- Immune Function analyses (response to PHA, pneumococcal vaccine or equivalent)
- Immunogenicity Revcovi antibody titers (i.e., neutralizing and binding antibodies) and anti-PEG antibodies (only if indicated)
- Quality of Life assessments

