Appendix 1: Suggested Schedule of Assessments for Adagen-Transitioning Subjects (cont.)

				HSCT or l	HSC-GT					
Procedure	TM 27 (±3 wk)	TM 30 (±3 wk)	TM 33 (±3 wk)	TM 36 (±3 wk)	TM 39 (±3 wk)	TM 42 (±3 wk)	TM 45 (±3 wk)	TM 48/ DC (±3 wk)	Month 1	Month 6
Informed assent/consent										
Demographics										
Medical history (including ADA- Mutation results if available)										
Inclusion/exclusion criteria										
Physical examination (including height and weight)	X	X	X	X	X	X	X	Х		
Vital signs	X	X	X	X	Х	X	X	Х		
Concomitant medications	Х	X	X	Х	Х	X	Х	Х		
Safety Laboratory Assessments (if available)	X	X	X	X	X	X	X	Х	X	X
Total trough erythrocyte dAXP		X		X		X		X		
Trough Plasma ADA activity ¹	X	X	X	X	X	X	X	X		
B-/T-/NK-lymphocyte subset	X	X	X	Х	X	X	X	Х		
Quantitative immunoglobulins		Х		Х		X		Х		
Immunogenicity ²	X	X	X	X	X	X	X	X		
Quality of Life										
Adverse events	X	X	X	X	X	X	X	Х	Х	X
Potential ADA inhibitors and Ig replacement therapy	X	X	Х	X	X	X	X	Х		
Revcovi Dosing and Compliance	X	X	X	X	X	X	X	X		

Subjects undergoing HSCT or HSC-GT will be followed one month and again at six months after final Revcovi dose to assess for AEs and survival.

Appendix 2:	Suggested Schedule of Assessment for Adagen-Naïve Subjects
-------------	--

	Enrollment	TW = Treatment Week									
Procedure	ENR	TW 2 (±3 d)	TW 4 (±3 d)	TW 6 (±3 d)	TW 8 (±3 d)	TW 10 (±3 d)	TW 12 (±3 d)				
Informed Assent / Consent	X										
Demographics	X										
Medical History	X										
Inclusion / Exclusion Criteria	X										
Physical Examination (including height and weight)	X	Х	Х	Х	Х	Х	Х				
Vital Signs	X	Х	Х	Х	Х	X	Х				
Concomitant medications	X	Х	Х	Х	Х	X	Х				
Safety Laboratory Assessments (if available)	X	Х	Х	Х	Х	X	Х				
Total Trough Erythrocyte dAXP	X	Х	Х	Х	Х	X	Х				
Trough Plasma ADA activity ¹	X	Х	Х	Х	X	X	Х				
B-/T-/NK-lymphocyte subset	X		Х		X		Х				
Quantitative immunoglobulins	X		Х		X		Х				
ADA-Mutation analysis (if available)	X										
Immunogenicity ²	X	Х	Х	Х	X	X	Х				
Quality of Life	X						X ³				
Adverse events		Х	Х	Х	Х	X	Х				
Potential ADA inhibitors and Ig replacement therapy	X	Х	Х	Х	Х	Х	Х				
Revcovi Dosing and Compliance	X	Х	Х	Х	Х	X	Х				

	TM = Treatment Month										
Procedure	TM 4 (±1 wk)	TM 5 (±1 wk)	TM 6 (±1 wk)	TM 7 (±1 wk)	TM 8 (±1 wk)	TM 9 (±1 wk)	TM 12 (±3 wk)	TM 15 (±3 wk)	TM 18 (±3 wk)	TM 21 (±3 wk)	TM 24 /DC (±3 wk)
Physical Examination (including height and weight)	X	X	X	X	X	X	X	X	X	Х	Х
Vital Signs	X	X	X	X	X	X	X	X	X	X	Х

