2. STUDY OBJECTIVES

2.1 **Objectives**

To conduct a registry study on patients, with adenosine deaminase severe combined immune deficiency (ADA-SCID) treated with Revcovi[®] and have periodic clinical and biochemical assessments for safety and dose adjustment based on adenosine deaminase (ADA) activity and erythrocyte deoxyadenosine nucleotide (dAXP) levels and/or clinical assessment by the treating physician. The study will include Adagen-naïve patients started on de novo enzyme replacement therapy (ERT) with Revcovi or converted from Adagen to Revcovi, over the course of 2 years and continued to be followed until the last enrolled patient has 2 years of follow up. Patients who are expected to receive 3 to 4 months of ERT prior to proceeding to hematopoietic stem cell transplantation (HSCT) or gene therapy will also be included in the study.

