4.2 As-Treated (AT) Population

The as-treated population, defined as all subjects who fulfill all eligibility criteria, had an informed consent form signed either by the patient or a legal guardian, are enrolled and receive at least one dose of Revcovi, will be the primary analysis set in all analyses. For the derivation of the AT population, the eligibility criteria will be used as collected in the eCRF.

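### SAP 8.8 presents the cumulative share of As-Treated subjects with a detected antibody as positivity at each visit, and no immunogenicity table shows how many were tested

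*SAP*

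**What the plan says.** SAP 8.8 (Immunogenicity) plans, for each antibody type, a percentage of positive subjects at every visit. Two rules define it:

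- Denominator: "Denominator for the calculation is the number of subjects in the AT population".
- Numerator: "Subjects who were tested as positive will be counted as positive for all subsequent visits".

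The same section plans a count of subjects who were positive at some time and later became negative, a listing of subjects whose positivity resolved, and a listing of all immunogenicity data. Sample collections and levels for positive tests are listed only.

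SAP 4.2 defines the AT population as eligible, consented subjects who "are enrolled and receive at least one dose of Revcovi, will be the primary analysis set in all analyses". It does not require an antibody test.

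The protocol makes testing conditional. Section 10.5.4 begins the sampling instruction with "If testing is necessary, venous blood samples for determination of anti-Revcovi binding and neutralizing antibodies". Sections 11.1 and 11.2 also limit testing to cases where it is indicated. The schedules in Appendices 1 and 2 nevertheless mark immunogenicity at most visits, while stating that they are a template and not a rigid requirement.

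Early departure is built into the design. SAP 2.1 includes "Patients who are expected to receive 3 to 4 months of ERT prior to proceeding to hematopoietic stem cell transplantation" or gene therapy. Protocol 7.1 follows subjects until the last enrolled patient reaches 24 months "or until undergoing HSCT or HSC-GT, whichever occurs first". After that, Appendix 1 states that they "will be followed one month and again at six months after final Revcovi dose to assess for AEs and survival", and neither appendix marks immunogenicity at those two contacts.

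**The concern.** A percentage shown for a visit is normally read as the share of subjects positive at that visit, among those who could be assessed. The SAP 8.8 figure is something else, and the table as planned does not let a reader see the difference. Tested and negative, not tested, and no longer followed all look the same in it.

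This matters because antibody status helps to interpret the biochemical results. Protocol 10.5.4 names antibody development as one possible explanation for a fall in ADA activity. Protocol 13.2.3.5 intends to examine how immunogenicity relates to biochemical endpoints and clinical toxicity. Both uses need to know who was tested and who is positive now.

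**Working it through.** The documents state no sample size, antibody rate or number tested, so there is no planned figure to reproduce. The check is on what the rule computes.

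**Step 1. The planned quantity.** Let N be the number of AT subjects (presumably within each status column, since SAP 5 reports by subject status and overall). Let C(v) be the number with at least one counted positive up to visit v. SAP 8.8 gives P(v) = C(v)/N. Carry-forward means that C(v) cannot decrease, and N is fixed, so P(v) cannot fall.

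**Step 2. Who counts as not positive.** The remaining N − C(v) subjects mix those tested and negative with anyone who has no earlier positive and who:

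- was never tested (Protocol 10.5.4, 11.1, 11.2);
- has left antibody follow-up, for example after HSCT or HSC-GT (Protocol 7.1, SAP 2.1);
- has not reached the visit;
- is an STP-2279-002 subject at a window before registry entry. SAP 13.3 counts that subject's Study Day 1 from the earlier study, but SAP 5 keeps that study's assessments out of the summary tables.

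**Step 3. Who stays in the numerator.** A subject with an earlier positive remains positive after a documented negative result and after leaving.

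**Step 4. Direction.** If recorded positives are true positives, undetected antibodies can only be missed, so C(v)/N is a lower bound on ever-positivity. If T subjects were ever tested, T ≤ N gives C/T ≥ C/N. Relative to current positivity there is no fixed direction: the full denominator pulls the figure down and carry-forward pushes it up.

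**Step 5. Illustration only.** Assume N = 30 and C = 3. Neither number is in the documents. The SAP figure is 3/30 = 10.0% in every row.

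| Assumed situation | Comparison figure |
|---|---|
| 6, 15, 24 or 30 ever tested | Ever-positive/ever-tested: 3/6 = 50.0%, 3/15 = 20.0%, 3/24 = 12.5%, 3/30 = 10.0% |
| 5, 10 or 15 have left; all others tested at the visit; the 3 positives remain and are still positive | Currently positive: 3/25 = 12.0%, 3/20 = 15.0%, 3/15 = 20.0% |
| As above, but the 3 positives are among those who left | Currently positive: 0/25, 0/20, 0/15 = 0% |
| Nobody has left; all 30 tested; 2 of the 3 now negative | Currently positive: 1/30 = 3.3% |

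**Step 6. Comparison within the SAP.** For infections, SAP 7.2.3 restricts the percentage denominator in each period to subjects with at least one day of observation in that period, and hospitalizations are handled similarly. SAP 8.8 makes no such restriction.

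**The case against.** The best defence is that the rule is disclosed. Section 8.8 states the measure, the denominator and the carry-forward together, and ever-positive over AT is a legitimate descriptive statistic. The listings and the became-negative count supply further detail. That stands: the arithmetic is not wrong, and the figure can be kept. But the became-negative count is not planned by visit, and the number tested would have to be rebuilt by hand from listings.

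It is also fair that a tested-only percentage is not automatically better. Protocol 10.5.4 has antibodies suspected after a persistent fall in ADA activity below 15 mmol/hr/L, so subjects tested on that trigger are selected and their rate probably overstates prevalence. This is why both percentages are needed.

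Four stronger readings are tempting and not supported:

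- *No table in the SAP shows how many subjects are under observation.* The SAP 7.2.3 denominators do so by yearly period. The n of the by-visit weekly-dose summary (SAP 8.7, with n required by SAP 5) approximates the number on treatment. The gap concerns numbers tested and currently positive.
- *Testing coverage is low.* The protocol makes testing conditional, but the schedules mark it at most visits. Coverage is unknown.
- *The number of visit windows after a 3-to-4-month stay measures the bias.* Windows up to TM 108 are template rows, not subjects. The documents do not say how many subjects are short-stay or which status group they belong to.
- *The planned figure understates positivity.* This holds for ever-positivity only. Against current positivity it can err either way.

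**Conclusion.** The concern holds as a matter of labelling and missing counts. Followed as written, SAP 8.8 produces a cumulative proportion of detected positives among AT subjects under a by-visit label, and no planned immunogenicity table gives the number tested or currently positive at a visit.

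The size cannot be computed from the documents. The illustrative percentages show only that the gap can be large and can go in either direction; they rest entirely on assumed counts, and the departure rows also assume that everyone remaining is tested. The lower-bound statement assumes that recorded positives are true. No hypothesis test is affected, because the study is descriptive, but the table should be corrected before the final outputs are produced.

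**What to change.** 1. Label the existing figure as cumulative ever detected positive among AT subjects.
2. Beside it, for each antibody type and subject status, show the number with a result in the visit window and the number positive among them, without carry-forward. Lead with counts, and include only visits with at least one result.
3. Report once, overall and not by visit, the number ever tested, the number never tested, and ever-positive/ever-tested. Add a note that subjects tested on indication are a selected group.

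A full grid of numbers under observation for every visit and status is not needed.

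The cost is a change of SAP wording and one larger table, using data already to be listed. Percentages on small per-visit denominators will be unstable, which is why counts should lead. The current-positivity figures may come out higher or lower than the one now planned.

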5.2 Description of the Study Product

Revcovi is approved by the FDA for the treatment of ADA-SCID in pediatric and adult subjects. Revcovi is a recombinant adenosine deaminase (rADA) based on bovine amino acid sequence, conjugated to monomethoxypolyethylene glycol (mPEG). rADA is manufactured in *E.coli* and is covalently conjugated to mPEG with a succinimidyl carbamate (SC) linker to produce methoxypolyethylene glycol recombinant adenosine deaminase. The approximate molecular weight of Revcovi is 113 KDa.

Revcovi was developed to replace the bovine-derived ADA in Adagen with recombinant ADA. Similar to Adagen, Revcovi provides an exogenous source of ADA enzyme that is associated with a decrease in toxic adenosine and deoxyadenosine nucleotides (dAXP) levels as well as an improvement in lymphocyte number and function.

The polyethylene glycol (PEG) used for manufacturing Revcovi is similar to the PEG used to manufacture Adagen. However, the succinimidyl succinate (SS) linker used to link PEG to ADA in Adagen has been replaced by the more stable SC linker in Revcovi.

The enzyme used for manufacturing Revcovi is recombinant and based on the same sequence as Adagen. Native bovine ADA undergoes post-transcriptional modification, with C-terminal processing (removal of the last six amino acids) and oxidation of cysteine at position 74 (Cys74). Therefore, rADA in SC-PEG rADA has been engineered so that the sequence encoding the last six amino acids of ADA have been deleted, and in addition, Cys74 has been mutated to serine (C74S), which reduces oxidative degradation of the molecule at this site without decreasing enzymatic activity of the protein.

Replacing Adagen with Revcovi eliminates any risk of transmission of transmissible spongiform encephalopathy (TSE) or adventitious mammalian viruses (e.g. bovine spongiform encephalopathy) to patients as well as guarantees a more consistent, stable, and indefinite supply of drug for the ADA-SCID patient population. Revcovi will also resolve the instability of Adagen (9-month shelf life) determined by the spontaneous dePEGylation during storage and protein degradation caused by the presence of protease impurities in the Adagen drug product. Additional details for Revcovi are provided in the Revcovi Package Insert (PI).

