13.2.3 Data Analysis

Statistical analysis will be conducted by Chiesi, or its designee. Analysis of study data will be performed after the last subject has completed assessments for the Treatment Month 24 Visit or, in the case of subject undergoing HSCT or HSC-GT, the 6 -month follow-up visit.

Statistical analyses will be performed using Statistical Analysis Systems® (SAS®) Version 9.4 or later (SAS Institute, Cary, NC), or comparable software.

A complete description of data handling rules and planned statistical analyses is detailed in a separate Statistical Analysis Plan. Unless otherwise specified in this document or in the Statistical Analysis Plan, baseline is defined as the last measurement for a variable before the initial dose of Revcovi, and missing data will generally not be imputed. Baseline for the patients transitioning from the Phase III STP-2279-002 study is the last available non-missing value prior to the initiation of Revcovi in the STP-2279-002 study.

Analyses will be descriptive, with data listings, graphical presentations, frequency tabulations, and summary statistics as appropriate.

Each subject will serve as his/her own control based on the baseline assessment of each endpoint as appropriate, including changes in body weight as percentile on the growth curve, antibody formation, etc.

Exposure and safety summaries will be presented by whether or not they previously participated in study STP-2279-002.

Additional statistical analyses, other than those described in this section, may be performed if deemed appropriate to further explore the study data.

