For the subjects transitioning from the STP-2279-002 study, the assessments during the STP-2279-002 study will be included in the data listings; however these assessments will not be included in the effectiveness or safety summary tables, because these results are already documented in the report of the STP-2279-002 study.

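### SAP 8.8 does not separate antibodies new on Revcovi from those present before it or of unknown baseline, and does not say whether STP-2279-002 positives count

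*SAP*

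**What the plan says.** SAP 8.8 sets the summary: "The percentage of subjects positive for each type of antibody will be summarized for each visit". It fixes the denominator: "Denominator for the calculation is the number of subjects in the AT population". It carries positives forward: "Subjects who were tested as positive will be counted as positive for all subsequent visits". It also counts subjects who turn negative after a positive, and lists all results. It defines no new or treatment-emergent antibody.

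Protocol 13.2.3 states: "Each subject will serve as his/her own control based on the baseline assessment of each endpoint as appropriate", and continues "including changes in body weight as percentile on the growth curve, antibody formation, etc".

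Protocol 11.1 lists antibody titers at enrollment, including "anti-PEG antibodies (only if indicated"). Enrollment items may be gathered retrospectively if available. On the two products, Protocol 5.2 says: "The polyethylene glycol (PEG) used for manufacturing Revcovi is similar to the PEG used to manufacture Adagen".

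For subjects from STP-2279-002, SAP 5 puts that study's assessments in the listings; "however these assessments will not be included in the effectiveness or safety summary tables". The reason given is that the STP-2279-002 report already documents them. SAP 13.3 nevertheless places both Study Day 1 and baseline for these subjects at the start of Revcovi in STP-2279-002.

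**The concern.** A reader of the immunogenicity table will want to know how many subjects developed antibodies on Revcovi. The protocol ties antibodies to falling trough ADA activity (6.3 and 10.5.4). It also plans to examine how immunogenicity relates to biochemical endpoints and toxicities (13.2.3.5), which requires knowing whether an antibody preceded Revcovi.

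The SAP makes this distinction elsewhere. It uses change from baseline for biochemistry, immune status, laboratory tests and vital signs, and a treatment-emergent definition for adverse events. Antibodies get neither, although Protocol 13.2.3 names them.

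Transitioning subjects come from chronic Adagen, which has a similar PEG and the same underlying enzyme sequence, so an antibody that predates Revcovi is plausible. STP-2279-002 subjects raise the opposite problem: an antibody formed on Revcovi in that study may never reach the summary.

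**Working it through.** The plan states no antibody rate, so there is no figure to reproduce. The check applies its rules to assumed counts.

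**1. Known baseline positives.** Take N = 20 transitioning subjects, E = 2 new positives on Revcovi and P pre-existing positives, all tested before Revcovi. SAP 13.3 gives every assessment an Enrollment/Baseline row, and the denominator is fixed.

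- P = 0: baseline 0/20, later 2/20 = 10%, difference 2/20.
- P = 4: baseline 4/20 = 20%, later 6/20 = 30%, difference 2/20.
- P = 8: baseline 8/20 = 40%, later 10/20 = 50%, difference 2/20.

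The later figure moves from 10% to 50%, but subtracting the baseline row always recovers the 2 new cases.

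**2. Pre-existing positives not tested before Revcovi.** Keep N = 20, P = 4 and E = 2. Let u of the 4 have no earlier test and first be found positive on Revcovi. They count as not positive at baseline, so:

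- baseline row = (P − u)/N
- later row = (P + E)/N = 6/20 = 30%
- apparent rise = (E + u)/N

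| u | Baseline row | Later row | Apparent rise |
|---|---|---|---|
| 0 | 4/20 = 20% | 30% | 2/20 = 10% |
| 2 | 2/20 = 10% | 30% | 4/20 = 20% |
| 4 | 0/20 = 0% | 30% | 6/20 = 30% |

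The number truly new is 2 in every row. If baseline status were known for all 20, the rate among baseline-negative subjects would be 2/(20 − 4) = 12.5%. The planned table cannot show which row applies, because it does not separate untested from tested negative.

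**3. STP-2279-002 subjects.** Assume 6 such subjects, with s of them positive on Revcovi in that study and negative or not retested in the registry. If SAP 5 governs, the summary shows 0/6 = 0%. Counted from the pre-Revcovi baseline, the figure is s/6: 16.7% for s = 1, 33.3% for s = 2 and 50.0% for s = 3. If SAP 8.8's carry-forward reaches back into that study, those positives are counted. Two programmers could follow the text and produce different tables.

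**4. How much follow-up is affected.** The clinical experience section of the protocol reports five subjects on Revcovi for over 135 weeks. Its heading is not visible in the supplied text, so it is an assumption that this is STP-2279-002. Then 135 × 7 = 945 days, which falls in the TM 30 window (868 to 958). With Study Day 1 set in that study, the SAP 5 exclusion could cover visits up to about TM 30 while these subjects stay in the denominator.

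**The case against.** The strongest reply is that little is lost. The baseline row and fixed denominator reveal new cases, as step 1 shows. That stands for subjects tested before Revcovi, and the 10% to 50% spread should not be read as the size of an error. It does not help subjects who were not tested. Appendices 1 and 2 do mark immunogenicity at enrollment, but by reference to the package insert and as a template rather than a requirement.

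A reader might infer three stronger things that the documents do not support:

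- **That the SAP attributes Adagen-era antibodies to Revcovi.** It reports percentages positive and makes no causal claim. Subject status is shown in separate columns, so the Adagen-naïve column is largely unaffected. Protocol 5.2 also describes a changed linker and a modified enzyme, and no document says whether the assays detect antibodies raised by Adagen.
- **That the SAP breaches the protocol.** The own-control rule is qualified by as appropriate, and Protocol 13.2.3.5 asks only that antibody results be summarized. SAP 8.1 declares no change, but the SAP was written to protocol Version 4.0 and the supplied protocol is Version 5.0. A false declaration is not shown.
- **That STP-2279-002 positives are lost.** They remain in the listings, the exclusion is deliberate and explained, and a subject who tests positive again in the registry is counted. No visible text reports an antibody positive in that study.

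The listings would let a careful reader classify subjects by hand. That does not remove the ambiguity in the summary table.

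**Conclusion.** The point holds in limited form. SAP 8.8 has no baseline comparison. For subjects without a pre-Revcovi test, a pre-existing antibody first detected on Revcovi cannot be told from a new one in the Adagen-transitioning and overall columns. For STP-2279-002 subjects, SAP 5, 8.8 and 13.3 do not fit together. If SAP 5 governs, a positive not repeated in the registry is missing from the summary while the subject stays in the denominator.

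The real size is unknown. The 10% to 30% apparent rise assumes 20 subjects, 4 pre-existing and 2 new positives, and that every pre-existing antibody is eventually detected. The 0% against 16.7% to 50.0% contrast assumes 6 STP-2279-002 subjects and 1 to 3 unrepeated positives. The analysis is descriptive and no hypothesis test is affected, but the change should be made before the final tables are produced.

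**What to change.** In SAP 8.8, classify each positive subject, per antibody type, as:

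- pre-existing: positive at the SAP 13.3 baseline;
- new since baseline: negative at baseline, positive later;
- baseline unknown: no test before Revcovi.

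Report new positives among subjects tested negative at baseline. Show the other two classes and the number tested in separate rows, and keep the planned AT-based percentage. For STP-2279-002 subjects, use the baseline from that study. Count positives that arose on Revcovi there in the summary, flagged as arising before the registry, and write this into SAP 5 as an exception.

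The cost is SAP wording and one table shell, using results already collected or listed. The new-positive rate will rest on subjects who happened to be tested before Revcovi, possibly a small and selected group, and the baseline-unknown row may be large. The fix cannot recover the status of untested subjects, but it makes that gap visible.
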